## **Comparison of the Results of Transcutaneous Carbondioxide and Oxygen Pressure in Premature Neonates Who Underwent Minimally Invasive Surfactant Therapy (MIST) Under Heated Respiratory Support With Nasal Cannula High Flow Air Support (HHHFNC) or Nasal Continuous Airway Pressure (CPAP) Methods**

### **Study Protocol:**

In premature babies (born before 37th week of pregnancy), surfactant production is insufficient since lung maturation has not been completed yet. Accordingly, surface tension increases in alveoli and it is difficult to keep the alveoli open, gas exchange is insufficient, and as a result, respiratory distress syndrome (RDS) occurs in premature babies. Severe respiratory failure occurs in the baby, it must be connected to the mechanical ventilator, even if hypoxia cannot be corrected, the baby may be lost. Intratracheal surfactant treatment is applied in the treatment of respiratory distress syndrome, which develops due to surfactant deficiency. With surfactant treatment, death due to RDS, mechanical ventilation requirement, morbidity due to lung disease, hospitalization times in neonatal intensive care units have been reduced and survival rates of premature babies have increased.

Intratracheal surfactant treatment is applied in RDS treatment. In recent clinical studies, two similar methods have been studied with a thin catheter without endotracheal intubation in the application of surfactant. One of these methods; Developed in Germany, it is LISA (the application of surfactant, which is less invasive), which is currently widely used in Europe. In the LISA method, surfactant is given after placing a thin flexible catheter into the trachea with the help of a laryngoscope (Magill's forceps may or may not be used) while the baby is in CPAP. The second method is the application of surfactant, which was developed in Australia and given by using a hard thin vascular catheter into the trachea while the baby is being followed up in CPAP only under direct laryngoscope without using forceps. This method is called MIST (minimally invasive surfactant treatment). In both methods, the aim is to give the surfactant warmed up to body temperature slowly in a few minutes with the help of an injector in a baby with spontaneous breathing under CPAP.

In the current RDS review (2019), it was emphasized that noninvasive respiratory support is the most appropriate way to support the breathing of preterm infants. Non invasive methods; CPAP is specified as bi-level CPAP, HHHFNC, positive pressure ventilation with nasal interval. CPAP devices provide gas flow under controlled pressure with probes firmly placed in the nose. Through the distension pressure; Supporting the opening of the upper airway, continued lung expansion and prevention of end-expiratory alveolar collapse (lung closure at the end of breath). Thus, it is easier to release the endogenous surfactant.

Heated high flow air support (HHHFNC) moistened with nasal cannula; It has been used as an alternative to nasal CPAP since 2013 RDS guideline. The utility mechanism allows the removal of carbon dioxide in the nasopharyngeal area, provides the anatomical dead space to be washed with air flow, reduces the disadvantage of the anatomical dead space. It also provides CPAP-like support thanks to its high flow rates. It reduces breathing work. It helps to reduce the FiO2 level, typically using a flow rate of 4-8 L / min.

According to the RDS review updated in 2019, early surfactant should be applied in infants with RDS. According to the latest recommendation, surfactant should be given if the baby's FiO2 (oxygen content in inhaled air) need is over 30%.

In our neonatal intensive care unit, respiratory support is given with nasal CPAP and HHHFNC instead of classical invasive (intubated) mechanical ventilation methods. In CPAP method, heated and humidified air is given a certain pressure (6-8 cmH2O), while in HHHFNC method, heated humidified

air is given at a certain flow rate (6-8 L / min). This study was planned to compare the results of infants who were given surfactant with MIST method under CPAP or HHHFNC support in the treatment of respiratory distress syndrome in premature babies. No blood will be collected from the babies included in this study, and nothing that will not be applied to babies who are not included in the study. If these babies need surfactant according to the chest X-ray and oxygen demand in the breathing air, surfactant support will be given by MIST method. In the follow-up of these babies, after the surfactant application, the follow-up application for each baby will be carried out; Blood gas will be taken in the second and sixth hour, and a chest radiograph will be taken in the sixth hour. The mechanical ventilation settings of the patient are made according to the values here. For example, the pressure given in case of insufficient oxygenation, the amount of oxygen is increased, the pressure given in case of hypercarbia is increased, the pressure is decreased in case of hypocarbia.

This measurement shows only partial carbon dioxide (PCO2) and partial oxygen (PO2) pressures in that instant blood gas. It is of great importance to protect the premature babies being monitored in the intensive care unit from hypoxia and hypercarbia, as well as the pressure, volume, oxygen-related trauma and injuries given by iatrogenically invasive or non-invasive respiratory support. Unnecessarily high supply of oxygen can cause oxygen radical damage and increase the risk of diseases associated with oxygen radical damage (premature retinopathy, necrotizing enterocolitis, bronchopulmonary dysplasia, periventricular leukomalacia). With the improvement of lung compliance and recovery of gas after surfactant treatment, carbon dioxide excretion may accelerate and hypocarbia may develop. Hypocarbia can cause intraventricular hemorrhage and periventricular leukomalacia in premature babies.

During surfactant application, babies will be monitored (as in all babies in the NICU) saturation, peak heart rate, perfusion index (the ratio of nonpulsatile flow in the capillary bed) and t values will be recorded. For all these reasons, monitoring of PI, PVI and continuous transcutaneous PCO2 and PO2 values are of great importance for the prevention of mortality and morbidity, as well as monitoring of oxygen saturation values with pulse oximetry in premature babies.

#### Research Method:

In our hospital, it was planned to take a total of 40 patients born under 32 weeks and less than 1500 grams (20 patients being in the HHHFNC, 20 patients in the CPAP group). Patients will be consecutively distributed to two groups until they reach the specified number of patients.

In this study, it was aimed to monitor continuous oxygen saturation, PI, PVI, transcutaneous PO2 and PCO2 measurements just before, during and after the surfactant application and to compare the results of babies who received nCPAP and HHHFNC support.

At the end of the study, all data will be entered in an SPSS file and study statistics will be made. A database will be created using SPSS software. A p value of <0.05 was determined as the limit of significance.

#### Inclusion criteria

- Premature babies under 37 weeks of sleep at Hacettepe University Neonatal Intensive Care Unit,
- Infants who have been diagnosed with respiratory distress syndrome in the first 24 hours of life, who have received surfactant treatment under the nCPAP or HHHFNC method using the MIST method,
- Babies whose informed consent was obtained from their mothers and / or fathers

#### Exclusion criteria

- Term babies born 37 weeks and over
- Babies monitored for intubation due to severe respiratory failure
- Babies with hemodynamically unstable, severe hypotension

Major congenital anomalies (severe congenital heart disease, congenital diaphragmatic hernia etc.)

- Babies with chromosomal disorders
- Babies with hereditary metabolic disease
- Babies whose informed consent form could not be obtained from their mothers and / or fathers
- Babies whose mothers have early membrane rupture or chorioamnionitis
- Diabetic mother babies
- Families who want their children to leave the work at any time of the study
- Babies whose study data cannot be collected completely

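### Two exclusion criteria, incomplete data and later family withdrawal, remove babies after they have been allocated and treated

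*Protocol*

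**What the plan says.** The Exclusion criteria section of the protocol lists "Babies whose study data cannot be collected completely" and "Families who want their children to leave the work at any time of the study" beside ordinary entry conditions such as congenital anomalies. Consent that was never given has its own line: "Babies whose informed consent form could not be obtained from their mothers and / or fathers".

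The Research Method section plans "20 patients being in the HHHFNC, 20 patients in the CPAP group" and fills the groups as follows: "Patients will be consecutively distributed to two groups until they reach the specified number of patients". The study readings (oxygen saturation, PI, PVI, transcutaneous PO2 and PCO2) are "measurements just before, during and after the surfactant application".

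The Inclusion criteria section admits infants "who have received surfactant treatment under the nCPAP or HHHFNC method using the MIST method".

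The protocol names no analysis set and does not say how a partial record is to be used.

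**The concern.** An exclusion criterion should be decidable before a baby enters a group. These two generally are not: they describe what happened to the baby or its record afterwards. Applied as written, they take out babies who were already distributed and treated, and the two supports are then compared only among those with a complete record and a family that stayed.

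That comparison is biased if the chance of being lost depends on gas exchange and also differs between the groups. One possible route is a baby who deteriorates on one support and whose monitoring is then interrupted; this is an inference, not something the protocol states. The direction cannot be known in advance. Because such babies count as excluded and the protocol does not ask for losses by group, a reader may be unable to tell harmless loss from harmful loss.

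This is not a matter of detail left to an SAP. The protocol states the rule, and an SAP that kept these babies would contradict the protocol's own exclusion criteria.

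**Working it through.** **1. When can each criterion be known?**

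| Line | Fact it needs | When it is known |
|---|---|---|
| Incomplete study data | Whether readings before, during and after surfactant were all obtained | Generally after allocation and treatment; a failure just before surfactant is the exception |
| Family withdrawal at any time | Whether the family later leaves | At any point to the end of the study; refusal at entry has its own line |
| Surfactant already received under one of the two supports (inclusion) | Treatment given | After treatment |

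The protocol also describes care after surfactant: "Blood gas will be taken in the second and sixth hour, and a chest radiograph will be taken in the sixth hour". If these count as study data, completeness is known only after six hours. The point does not depend on that, because the transcutaneous readings alone extend past surfactant.

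**2. Size.** The protocol gives no effect size, SD or loss rate. Its only figure to check is 20 + 20 = 40, which agrees. What follows is an illustration.

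Taken from the protocol: 20 per group and a significance limit of 0.05. Assumed: two-sided testing, a t-test, no true difference, outcome Y normal with SD 1 in both groups, worst values lost, and the loss rates shown.

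A baby is lost if L = ρY + √(1 − ρ²)E exceeds the cut-off c that gives loss rate l. E is independent standard normal and ρ is the correlation between loss and outcome. The false difference between completers, in SD units, is

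ρ × [φ(c₁)/(1 − l₁) − φ(c₀)/(1 − l₀)].

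- l = 5%: c = 1.645, φ(c) = 0.1031, 0.1031/0.95 = 0.109
- l = 10%: c = 1.282, φ(c) = 0.1755, 0.1755/0.90 = 0.195
- l = 20%: c = 0.842, φ(c) = 0.2800, 0.2800/0.80 = 0.350

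At ρ = 1, 0% versus 5% gives 0.109; 5% versus 10% gives 0.195 − 0.109 = 0.086; 10% versus 20% gives 0.350 − 0.195 = 0.155. At ρ = 0.5 each is halved.

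Type I error from 400,000 simulated trials per cell, 20 completers per group:

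| Loss, group A vs B | Shift (SD), ρ = 1 / 0.5 / 0 | Type I error, ρ = 1 / 0.5 / 0 |
|---|---|---|
| 5% vs 5% | 0 / 0 / 0 | 5.0 / 5.0 / 5.0% |
| 10% vs 10% | 0 / 0 / 0 | 5.0 / 5.0 / 4.9% |
| 0% vs 5% | 0.109 / 0.054 / 0 | 6.2 / 5.3 / 5.0% |
| 5% vs 10% | 0.086 / 0.043 / 0 | 6.0 / 5.2 / 5.0% |
| 10% vs 20% | 0.155 / 0.077 / 0 | 9.1 / 5.7 / 5.0% |

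**3. If the 20 are counted at allocation and lost babies are simply dropped**, the type I error at ρ = 1 / 0.5 is 6.1 / 5.3% for 0% versus 5%, 5.9 / 5.2% for 5% versus 10%, and 8.3 / 5.6% for 10% versus 20%. Whether lost babies are replaced therefore changes little. The protocol's wording on filling the groups permits replacement without stating it.

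A separate simulation (40,000 runs) removed the most extreme babies from one tail of one group only. Losing one of 20 gave about 7% and two of 20 about 10%. That is a deliberate worst case and shows sensitivity, not an expected bias.

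**The case against.** The data line can be read more mildly, as covering babies in whom monitoring is foreseeably not feasible. That would be a proper entry condition, and a sensor failing just before surfactant would be noticed in time. The protocol does not say when the line is applied. The withdrawal line may only express the parents' right to leave, put in the wrong list. The moment of allocation is not stated either, and the inclusion line's past tense may be an effect of translation. Analysis sets and the use of partial readings commonly belong in an SAP. The computed effects are also modest and rest on assumed loss rates.

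Much of this is fair, but it does not remove the point. The milder reading explains some failures of data collection; it cannot cover withdrawal at any time, given that missing consent has its own line. A right to withdraw is proper, but as an exclusion criterion it also discards the readings already taken. The protocol says patients are distributed to two groups, which describes assignment, and an inclusion line conditional on treatment received repeats the fault. The choice of model and of any sensitivity analysis can indeed wait for the SAP; the eligibility wording cannot. That the effects are modest bears on the weight of the point, not on whether it holds.

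**Conclusion.** The concern holds and should be fixed. That the wording removes babies after allocation is clear from the text, with the reservation that some data failures may be noticed before treatment. A completers-only comparison is the effect of following these lines, not a stated analysis rule.

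Whether bias results is unknown. There is none, when the supports truly do not differ, if loss is technical or equal in both groups. Under mild unequal loss the type I error rises from 5% to about 6% at most. It reaches about 9% only if loss is heavy, unequal and fully outcome-driven (10% versus 20%). The inclusion line is the same kind of fault but was not modelled, and it adds nothing to these figures.

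**What to change.** - Delete the two lines from the exclusion criteria and put the parents' right to withdraw in a separate paragraph.
- Reword the inclusion line on surfactant already received so that eligibility rests on facts known before allocation.
- State when allocation takes place, and count the 20 per group at that moment.
- Analyse every allocated baby in the allocated group with the readings obtained up to loss, subject to parental consent.
- Report the number of losses and their reasons by group.

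The model and any sensitivity analysis can stay with the SAP.

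The cost is the wording of three eligibility lines, a sentence on allocation and one table; no measurement is added. The downside is that complete records may fall below 20 per group: 20 × 0.95 = 19 versus 20 × 0.90 = 18 at an assumed 5% versus 10% loss, and 20 × 0.90 = 18 versus 20 × 0.80 = 16 at 10% versus 20%.
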